1.1 Background and Relevant Research

1.1.1 Neurodegeneration in PPA variants

Specific language deficits that emerge in persons with different PPA variants relate to the regions of the left hemisphere language networks that are selectively affected by neurodegeneration (Grossman, 2010). Atrophy is observed in the left inferior frontal lobe and insula in persons with naPPA. Individuals with lvPPA show atrophy of the left posterior temporal and parietal lobes. Semantic variant PPA (svPPA) involves atrophy of the anterior and ventral temporal lobe (Grossman, 2012; 2018; Agosta et al., 2013; Giannini et al., 2017). Thus, each PPA syndrome affects a portion of the neural network supporting language, while other portions of the language network remain relatively preserved. Unfortunately, while our expanding understanding of the anatomic, neural, and functional properties of language networks has enabled greater insight into the neural changes that underlie PPA symptoms, there are no approved therapies that leverage this knowledge in order to advance targeted treatments for neurodegenerative aphasias.

1.1.2 tDCS to treat PPA

Transcranial direct current stimulation (tDCS), a noninvasive brain stimulation technique, is a promising intervention in aphasia. TDCS delivers low-intensity electrical current to the brain through electrodes placed on the scalp. This low-intensity current can produce small shifts in the resting membrane potential of large numbers of neurons which is believed to alter neuronal firing rates and thus modulates patterns of brain activity (Bindman et al., 1964; Stagg & Nitsche, 2011; Rahman et al., 2013). Evidence indicates that repeated stimulation with tDCS can result in lasting changes in cognitive performance (e.g. Ries et al., 2009; Flöel et al., 2012). A number

CONFIDENTIAL

of studies indicate that tDCS may serve as an effective intervention for aphasia (Reviewed in Norise & Hamilton, 2017). In our own prior work, we found that 10 days of tDCS in subjects with post-stroke aphasia resulted in a ~17% improvement in aphasia severity, compared to sham tDCS. This improvement was measured two months after discontinuation of stimulation (Shah-Basak et al., 2016).

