8.4.3 Network Neuroscience measures of response to tDCS + CILT

We will first test for the hypothesized relationship between node loss and hub scores by expressing node loss as a quadratic term in a multiple regression using the gray matter thinning at each node in the language network to predict hub scores, covarying for subject age and disease onset, with an FDR-corrected threshold of 0.05. Then, we will use a data-driven machine learning approach—support vector regression—using multivariate hub scores (Fornito et al., 2015) throughout the brain to predict behavior. We will use a leave-one-out cross validation strategy to identify the combination of nonlinearly weighted variables that predict behavior. The value of the machine learning model will be evaluated in terms of percentage of variance explained relative to selecting a similarly sized set of random variables (neuroimaging features including region cortical thickness and individual white matter connections) in 10,000 permutations for both the traditional regression and support vector regression models. It will additionally be tested against network density—the total connectivity of the network—as a control condition. Then, to test whether strong hubs account for the greatest variance in the data, we will correlate the support vector regression weights with region hub scores post-hoc. A significant positive correlation would indicate that stronger hubs account for higher variance in behavioral scores.

We will then use multiple regression to assess stimulation condition as a predictive variable for each language network node. If the predictor illustrates that hub scores increase in the presence of active tDCS, we will test whether effects tend to be concentrated near the site of

CONFIDENTIAL

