stimulation using a permutation test in which we shuffle the assignment of significant nodes for each network statistic uniformly at random across the brain. If the number of nodes concentrated in the anterior perisylvian nodes encompassed by our area of stimulation is greater than 95% of permutations, it will establish that the effects of mCILT or tDCS + mCILT are local to this region. Moreover, it will allow us to examine whether the effects of stimulation on hub scores are observed in different PPA phenotypes that express pathology at the site of stimulation (as in our nPPA/lvPPA subject) or remote from the site of stimulation (as in our svPPA subjects). Finally, to test if patterns of hub scores across the brain distinguish pre-from post-treatment, we will train support-vector classifiers in a leave-one-out fashion to distinguish pre-and post-treatment conditions within each phenotype using all node hub scores. We will use permutation testing to examine the accuracy of the classifiers against 10,000 null permutations to examine the significance of our results. Further exploratory analyses will examine the specific effect of mCILT alone on language network properties.

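### The test of whether tDCS effects are local shuffles significant nodes over the whole brain although only language-network nodes were tested, so its false-local rate can exceed the implied 5%

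*Combined protocol and SAP*

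**What the plan says.** All the relevant steps are in section 8.4.3 of the combined protocol and SAP.

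- **Nodes tested.** "We will then use multiple regression to assess stimulation condition as a predictive variable for each language network node".
- **When the locality test runs.** Only if those regressions show hub scores rising under active tDCS.
- **Null distribution.** In the permutation test, "we shuffle the assignment of significant nodes for each network statistic uniformly at random across the brain".
- **Decision.** If the count of significant nodes in the anterior perisylvian area under the electrode "is greater than 95% of permutations, it will establish that the effects of mCILT or tDCS + mCILT are local to this region".
- **Use.** The result is also meant to inform a comparison between variants whose pathology lies at the stimulated site and those whose pathology lies away from it.

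The section gives no number of brain, language-network or perisylvian nodes, and does not say how many perisylvian nodes belong to the language network. Nothing extends the stimulation regression to the whole brain, and nothing limits the shuffle to the tested nodes. Where other steps use the whole brain, the section says so: the support vector regression takes hub scores from throughout the brain, and the classifiers are to "distinguish pre-and post-treatment conditions within each phenotype using all node hub scores".

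**The concern.** A permutation null should move labels only among units that could have carried them. Here only language-network nodes can become significant, but the shuffle spreads the labels over every node. The comparison then mixes two questions: whether the effect is concentrated within the tested network, and whether the tested network is itself concentrated near the electrode. The second is settled by the choice of nodes before any data are seen.

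The error favours a finding of locality whenever perisylvian nodes make up a larger share of the tested set than of the brain. Section 1.1.1 makes some overlap plausible: "Atrophy is observed in the left inferior frontal lobe and insula in persons with naPPA", and "each PPA syndrome affects a portion of the neural network supporting language". Neither statement fixes how large the overlap is.

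At stake is the mechanistic conclusion. The plan treats a pass as establishing a local effect and carries it into the comparison of variants. As written, a pass could reflect which nodes were tested rather than where stimulation acted.

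**Working it through.** **Inputs.** From section 8.4.3: the tested set is the language network, the shuffle set is the brain, and the observed count must exceed 95% of permutations (an implied one-sided 5%; no alpha is stated). Assumed, because the documents give none of them: *N* brain nodes, *L* language nodes, *A* perisylvian nodes, *o* of those *A* inside the language network, and *k* significant nodes. The example uses *N* = 200, *L* = 30, *A* = 10, *k* = 6.

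**Formulas.** A uniform shuffle makes the perisylvian count hypergeometric.

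- Critical count *c*: the smallest *c* with P(X < *c*) ≥ 0.95, X ~ Hypergeom(*N*, *A*, *k*).
- False-local rate: P(Y ≥ *c*), Y ~ Hypergeom(*L*, *o*, *k*). This describes significant nodes spread evenly over the tested network, with no locality within it.
- Restricted shuffle: the same rate, with *c* taken from Hypergeom(*L*, *o*, *k*).

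**Step 1: the implied 5%.** Under the whole-brain null:

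- P(X = 0) = C(190,6)/C(200,6) = 0.732
- P(X = 1) = 10 × C(190,5)/C(200,6) = 0.237
- P(X < 2) = 0.970, so *c* = 2

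If significant nodes could fall anywhere in the brain, the rate would be 1 − 0.970 = 3.0%, so the rule would keep its level.

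**Step 2: significant nodes can arise only in the language network.** The whole-brain null expects 6 × 10/200 = 0.3 perisylvian hits. With full overlap, even spread over the tested nodes gives 6 × 10/30 = 2.0, which already equals the critical count. Then:

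- P(Y = 0) = C(20,6)/C(30,6) = 38,760/593,775 = 0.065
- P(Y = 1) = 10 × C(20,5)/C(30,6) = 155,040/593,775 = 0.261
- False-local rate = 1 − 0.065 − 0.261 = 0.674

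**Step 3: vary the overlap.**

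| Perisylvian nodes in the language network (of 10) | Expected hits under even spread | Whole-brain shuffle, *c* = 2 | Restricted shuffle |
|---|---|---|---|
| 10 | 2.0 | 67% | 0.9% (*c* = 5) |
| 7 | 1.4 | 43% | 1.6% (*c* = 4) |
| 5 | 1.0 | 25% | 4.1% (*c* = 3) |
| 3 | 0.6 | 9% | 0.5% (*c* = 3) |
| 2 | 0.4 | 3% | 3.4% (*c* = 2) |

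**Step 4: vary everything.** The grid was *N* = 114, 200, 400; *L* = 20, 30, 40; *A* = 6, 10, 15; *k* = 2, 3, 4, 6, 10; overlap 30, 50, 70, 100% of *A*, rounded half up. That is 3 × 3 × 3 × 5 × 4 = 540 settings. The whole-brain rate runs from 0% to 100%, with median 16%; it exceeds 5% in 408 settings and 50% in 101.

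| Overlap | Median rate | Settings above 5% |
|---|---|---|
| 30% | 3.6% | 59 of 135 |
| 50% | 14% | 101 of 135 |
| 70% | 26% | 117 of 135 |
| 100% | 47% | 131 of 135 |

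With only 2 significant nodes the median is 6%. The restricted shuffle never exceeds 5.0%. Rounding half to even instead gives a median of 15%, with 397 settings above 5% and 94 above 50%.

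**Step 5: a limiting case.** In the example network, let all 30 language nodes be significant, an effect across the entire tested set. The whole-brain critical count is then 4. The rule declares locality with certainty if 10 or 5 perisylvian nodes are language nodes, but not if only 3 are.

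**The case against.** **The size is assumed.** Inflation needs perisylvian nodes to be over-represented in the tested set, and 525 of the 540 settings have that property by construction. The grid therefore shows how the rate behaves, not how likely the problem is in this trial. At 30% overlap, 76 of 135 settings stay at or below 5%. With 2 significant nodes in the example network, the rate is 10.3% at full overlap, 4.8% with 7 of 10 and 2.3% with 5 of 10. This stands: the level is not controlled, but the actual rate is unknown.

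**The overlap evidence is partial.** Section 8.4.3 places naPPA and lvPPA pathology together at the stimulated site, but section 1.1.1 puts lvPPA atrophy in the posterior temporal and parietal lobes. Only the naPPA half supports anterior overlap. This also stands, and it weakens the case for the highest rates.

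**The wording may be loose.** The authors may have meant to test nodes over the whole brain, or to shuffle only the tested nodes. Either reading would keep the level. The literal text supports neither, because the section distinguishes the two node sets elsewhere, and either intention needs the same short edit.

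**The consequence is limited.** The test runs only after a positive result and addresses where an effect lies, not whether there is one. That limits the importance of the point but does not correct the test.

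**Conclusion.** The concern holds. As written, the significant nodes come from one set and the null from a larger one, and nothing in the documents reconciles them. The 95% rule therefore does not hold the false-local rate at 5%.

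The size depends on four node counts and an overlap that the plan does not state. In the worked example the rate falls from 67% to 3% as the overlap falls from 10 to 2 of 10 nodes, so low overlap or few significant nodes can keep it under 5%. The safe conclusion is that the rate can exceed 5%, by a wide margin if most perisylvian nodes are language nodes. The point should be corrected before the imaging analysis, but it is confined to a secondary mechanistic objective. The WAB-AQ comparison of real with sham tDCS does not depend on it.

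**What to change.** In section 8.4.3, choose one of these:

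1. Permute the significant labels uniformly among the language-network nodes entered in the stimulation regression, and only those.
2. Fit the stimulation regression at every brain node first, with multiplicity correction over all of them, and keep the whole-brain shuffle.

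Under either option, state the number of nodes tested, the number of anterior perisylvian nodes and how many of these are among the tested nodes. Describing a pass as supporting locality rather than establishing it would also be more measured, but that is a matter of wording and does not repair the test.

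**Cost.** One or two sentences and a one-line code change, with no change to data collection. Option 1 declares locality less often and is conservative when few nodes are significant. In the example network with full overlap, 2 significant nodes could never pass (the critical count is 3), and with 3 or 4 every one would have to be perisylvian. Option 2 avoids that restriction but adds tests to correct for.

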1.1.4 Using brain networks to predict tDCS response

Evidence points toward the importance of brain network hubs—nodes that are connected to many other nodes by edges—in neurodegenerative disorders. Nodes with high hub centrality are critical participants in a wide range of network operations supporting cognitive functions (van den Heuvel & Sporns, 2013) and are disproportionately affected in neurological syndromes (Stam, 2014). The tendency for a node to be a hub can be distinguished from more general measures such as network density, the total number of connections in a network, and can be expressed as a hub score, which quantifies the centrality of a node in information processing in a network (van den Heuvel, 2010). Brain regions with especially high hub scores participate in many processing pathways within the brain. Across the spectrum of neurodegenerative disorders, it is suspected that as nodes in critical brain areas are progressively degraded by disease, this is associated with changes in the recruitment of remaining hub nodes (Stam, 2014). Early in the course of degenerative disease, as specific brain regions are selectively affected, it is believed that there is an *increase* in the connectivity of remaining hubs in those regions that partially compensates for lost nodes and helps to maintain performance (Stam, 2014). However, as worsening disease leads to greater node loss, these compensatory changes cannot keep pace with neurodegenerative deterioration, resulting in decreasing hub scores in affected regions (Buckner et al., 2009; Engels et al., 2015). Eventually, when degenerated regions are severely affected, hub scores decline dramatically as the few remaining nodes do not harbor sufficient connections to contribute to networks. In the case of PPA, residual language abilities would then depend on the activity of relatively spared language regions. In a preliminary analysis of 65 subjects with PPA we found that hub scores are indeed decreased in different language centers in PPA variants. Thus, the hub score could serve as a metric in PPA to describe how affected and spared regions impact network functions at different stages of disease. Brain network hubs could also be positively influenced by interventions that enhance their connectivity. We posit that changes in hub scores could also provide a framework for understanding the impact of tDCS on language networks in persons with PPA.

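### The locality test shuffles labels over the whole brain although only language network nodes are tested, and it ignores spatial correlation, so a diffuse language-network effect can be called local well above the nominal 5%

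*Combined protocol and SAP*

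**What the plan says.** Section 8.4.3 sets out three steps.

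- **Node-wise test.** Multiple regression is used to "assess stimulation condition as a predictive variable for each language network node".
- **Gate.** The locality test follows only under the condition "If the predictor illustrates that hub scores increase in the presence of active tDCS".
- **Locality test.** The plan will "shuffle the assignment of significant nodes for each network statistic uniformly at random across the brain". The statistic is "the number of nodes concentrated in the anterior perisylvian nodes encompassed by our area of stimulation". If it exceeds 95% of permutations, "it will establish that the effects of mCILT or tDCS + mCILT are local to this region".

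The section then says that the result will let the team examine stimulation effects in variants whose pathology lies at the site or remote from it. Neither this section nor the rest of the statistical plan describes a spatially constrained null, cluster-level inference or any other allowance for correlation between nodes.

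**The concern.** A permutation test has its stated error rate only if the shuffled arrangements are as likely as the observed one when the hypothesis of interest is false. Because of the gate, the relevant null here is that stimulation has an effect but the effect is not concentrated at the site. The uniform shuffle misrepresents that null in two ways.

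- **Wrong set of nodes.** Only language network nodes can be labelled significant, but the shuffle spreads the labels over the whole brain. Any effect confined to the language network then looks concentrated in a region that belongs to that network.
- **No spatial structure.** Section 1.1.4 describes hubs as "nodes that are connected to many other nodes by edges", so scores of nearby regions are unlikely to vary independently. Neighbouring nodes then cross the threshold together. The count in a contiguous region varies more than a scattered shuffle allows, and the upper 5% of the permutation distribution is reached too often.

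At stake is the study's statement about where tDCS acts, and the comparison of variants that leans on it.

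**Working it through.** **Inputs.** From section 8.4.3: the uniform whole-brain shuffle, the 95% rule, and testing at language network nodes. Assumed, because the documents are silent: N nodes in the brain, L tested language nodes, R nodes in the region (taken to lie wholly inside the tested set), k significant nodes, and the correlation between neighbours.

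**1. The plan's own figure.** The rule implies a one-sided error of 1 − 0.95 = 0.05. Under a uniform shuffle the regional count X is hypergeometric:

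P(X = x) = C(R, x) · C(N − R, k − x) / C(N, k),

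and the effect is called local if P(X < observed) > 0.95. Take N = 200, R = 10, k = 5. Then P(X = 0) = 0.772 and P(X ≤ 1) = 0.979, so a count of 2 suffices and the attained error is 1 − 0.979 = 0.021. In simulation with independent nodes, all of them tested, the rate was 0.9–3.0%. Under its own assumptions the test stays within 5%; it falls below because counts are discrete.

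**2. Whole-brain shuffle, nodes independent.** Suppose only L = 40 of the 200 nodes are tested and the 5 significant ones are spread evenly among them. The shuffle expects 5 × 10/200 = 0.25 in the region; the true expectation is 5 × 10/40 = 1.25. The chance of reaching 2 is

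1 − [C(30,5) + 10 · C(30,4)] / C(40,5) = 1 − (142,506 + 274,050)/658,008 = 0.367.

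The same calculation for other settings gives these false-local rates:

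| N, L, R | k = 3 | k = 5 | k = 8 | k = 12 |
|---|---|---|---|---|
| 200, 60, 10 | 6.9% | 19.0% | 12.0% | 31.6% |
| 200, 40, 10 | 14.9% | 36.7% | 31.2% | 64.5% |
| 400, 60, 20 | 25.5% | 54.5% | 53.9% | 84.8% |

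Shuffling within the L tested nodes instead gives 0.4–4.6% over the same settings. In simulations that let k vary, with 40 of 200 or 60 of 400 nodes tested, the whole-brain shuffle gave 3.8% and 11.3% with no effect, and 40.5% and 74.1% with a diffuse effect.

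**3. Correlation alone, all N nodes tested.** Null maps were Gaussian fields on a sphere with exponentially decaying correlation, 6,000 maps with 20 placements of the region. A node was significant at z > 1.96. The diffuse effect is a mean z of 1 at every node, the situation the gate selects for. For N = 200, R = 10:

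| Neighbour correlation | Uniform shuffle, diffuse effect | Uniform shuffle, no effect | Region relocation, diffuse effect |
|---|---|---|---|
| 0 | 2.4% | 1.7% | 2.2% |
| 0.30 | 6.6% | 2.8% | 2.7% |
| 0.55 | 10.7% | 4.0% | 3.0% |
| 0.74 | 12.9% | 5.3% | 2.8% |

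Over all layouts run, with correlations of 0.30–0.81, the rate was 6.3–18.1% with a diffuse effect and 2.2–7.7% with none. A further simulation under different assumed settings gave 11–20% and 6–11%.

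**4. Both faults need repair.** Shuffling within the tested nodes but ignoring correlation still gave up to 9.3%.

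**5. Alternatives under a diffuse effect.** Relocating the intact region gave 1.4–3.8% over all 16 scenarios on the sphere (with and without an effect) and 1–3% in the further simulation. Sign-flipping real-minus-sham maps with an inside-minus-outside mean-effect statistic gave 2–6% in one simulation and 6–8% in another.

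**The case against.** Four points can be made for the plan.

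- **The size rests on assumptions.** This stands. A reader might infer that the test always over-rejects. The documents do not support that: with independent nodes the correlation problem vanishes, and with weak correlation or few significant nodes the rate can stay at or below 5%.
- **The gate screens out chance findings.** A reader might infer that pure noise would often be reported as a local effect. The locality test runs only after hub scores are seen to rise with active tDCS. Section 8.4.3 also gives an FDR-corrected 0.05 threshold for its earlier node-loss regression. If that threshold carries over, which is not stated, a simulation with no effect anywhere gave at most 0.3%. The problem is a real but diffuse effect being called local. FDR control does not cure that, because the shuffle starts after nodes have been labelled.
- **The authors may intend to test every brain node.** Other analyses in the section use hub scores throughout the brain. If that is the intention, the first fault disappears and the correlation fault remains. The text as written limits the node-wise test to the language network.
- **It is secondary.** This stands. A reader might infer that the efficacy conclusion is at risk, but the WAB-AQ comparison in sections 8.1 and 8.4.1 does not use this test. Section 2.2 does not list locality as an objective of its own, and the variant comparison is something to be examined, not a decision rule.

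**Conclusion.** The concern holds for the case that the gate selects: an effect present in the language network but not concentrated at the site. There the 95% rule does not deliver 5% error. The whole-brain shuffle is the clearer fault, since it is visible in the text and needs no correlation assumption. It alone gives from about 8%, or less when very few nodes are significant, to over 50%. Spatial correlation alone gives about 6–20%, against 2–3% for independent nodes. All these figures depend on assumed node counts, region sizes and correlations and show a plausible range, not an estimate for this trial. A test with this property cannot bear the statement that it establishes locality. The change should be made before unblinding, as a correction to a secondary mechanistic analysis.

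**What to change.** Amend section 8.4.3 as follows.

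1. State which nodes are tested, their number, the nodes that make up the stimulation region, and the node-wise significance threshold.
2. Draw the null from the tested nodes only.
3. Use a null that keeps spatial structure and targets an effect that is present but not concentrated. Either:
   - relocate the intact perisylvian region across the tested nodes and compare its count of significant nodes with the counts at the other positions; or
   - sign-flip each participant's real-minus-sham map, using the inside-minus-outside difference in mean effect as the statistic.
4. Say that a positive result will support locality, in place of establishing it.

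Do not combine sign-flipping with counts of significant nodes. That null means no effect anywhere, so a diffuse effect beats it in every region: simulated false-local rates were 56–94% for the inside count and 20–22% for the inside-minus-outside proportion.

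The cost is computing time and SAP wording; no new data are needed. Relocation may be coarse if few nodes are tested. With M positions including the true one, exceeding more than 95% of them requires (M − 1)/M > 0.95, so M must exceed 20. A 40-node network with one placement per node offers at most 40 overlapping positions. The relocation rates above come from moving the region over all N nodes, so the chosen method should be checked by simulation on the actual parcellation before unblinding.

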8.3 Sample Size and Power Determination

To calculate power, we started from an ambitious but realistic estimate of the population available at the participating recruitment sites. We intend to recruit 62 subjects, although 25 subjects will be adequate to detect a difference between real and sham stimulation within each group (alpha = 0.05; power = 0.8). Although our historical attrition rate has been 15%, we will conservatively anticipate a 25% attrition rate and will therefore enroll 31 subjects in each PPA variant arm.

CONFIDENTIAL

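### The locality test in 8.4.3 counts significant language-network nodes against a whole-brain label shuffle: it can report a diffuse effect as local, and thresholding can cost power

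*Combined protocol and SAP*

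**What the plan says.** The locality analysis in section 8.4.3 has four steps.

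1. One model per node, for language nodes only: "We will then use multiple regression to assess stimulation condition as a predictive variable for each language network node".
2. A gate, so that the locality test runs only on a favourable result: "If the predictor illustrates that hub scores increase in the presence of active tDCS".
3. A null distribution from a "permutation test in which we shuffle the assignment of significant nodes for each network statistic uniformly at random across the brain".
4. A decision rule on a count: "If the number of nodes concentrated in the anterior perisylvian nodes encompassed by our area of stimulation is greater than 95% of permutations". Passing is taken to establish that the effect is local, and the result then feeds a comparison of the PPA phenotypes.

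The section does not give the node-level significance threshold for this step, the atlas, the number of language nodes, or the number of nodes at the site. The phrase "with an FDR-corrected threshold of 0.05" belongs to the earlier regression of hub score on node loss. Section 8.3 sizes the behavioural comparison only.

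**The concern.** Two features of the test pull in different directions.

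**The reference set does not match the tested set.** Labels can arise only at language-network nodes, but the shuffle spreads them over all brain nodes. The site lies inside the language network, so any effect spread across that network puts more labels at the site than the shuffle expects. The test then largely asks whether the effect lies in the language network, which the choice of tested nodes has already settled. It does not ask whether the effect is larger at the site than in the rest of the network.

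**The statistic discards effect size.** Each node yields a continuous real-versus-sham effect, but only its label is used. A sub-threshold effect at the site counts as zero, and a node just under the threshold counts the same as one far beyond it.

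At stake is a mechanistic conclusion under the network objectives in section 2.2: whether stimulation acts near the electrode, and whether this differs between naPPA/lvPPA and svPPA.

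**Working it through.** The plan gives no power, effect size or node count for this test, so there is no figure of its own to reproduce.

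**Inputs from the plan**
- Completers: 31 enrolled per variant with 25% attrition (section 8.3) gives 31 × 0.75 = 23.25, so N = 23 per variant and 46 in all.
- Reference effect: 25 subjects at 80% power and alpha 0.05 (section 8.3) imply, for a paired comparison, d = (1.960 + 0.842)/√25 = 0.56, or about 0.58 with the t distribution. This is a behavioural effect. The node effect is unknown, and 0.57 serves only as a marker.

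**Assumptions**
- 40 language nodes, 10 at the site, in a 200-node brain.
- Effects in SDs of the within-person real-sham difference.
- Nodes labelled at uncorrected p<0.05 or at FDR 0.05.
- Nodes independent, exchangeably correlated (0.3), or correlated between neighbours (up to 0.6).

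**Step 1: why the whole-brain shuffle favours the site.** Suppose 20 of the 40 language nodes are labelled, evenly spread. The site then holds 20 × 10/40 = 5.
- Whole-brain shuffle: expected count 20 × 10/200 = 1. The hypergeometric chance of 5 or more is 0.001, so the effect is declared local.
- Shuffle over tested nodes: expected count 20 × 10/40 = 5. The chance of 5 or more is 0.64, so it is not.

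The site is no different from the rest of the language network, yet the written rule rejects. The expected count is too small by a factor of 200/40 = 5.

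**Step 2: how often a diffuse effect is declared local** (equal effect at all language nodes, written shuffle, nominal 5%)

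| Diffuse effect | Uncorrected labels | FDR labels |
|---|---|---|
| 0.2 SD | 33-56% | – |
| 0.3 SD | 57-91% | 21-72% |
| 0.4 SD | 74-100% | – |

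**Step 3: power when the effect is truly local** (count test with the shuffle restricted to tested nodes, against a site-minus-rest contrast per participant; independent or exchangeable nodes)

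| Site / elsewhere | N | Count, uncorrected | Count, FDR | Contrast |
|---|---|---|---|---|
| 0.2 / 0 | 23 | 15-17% | about 1% | 82-93% |
| 0.2 / 0 | 46 | 42-48% | 2-5% | 98-100% |
| 0.3 / 0.1 | 46 | 74-77% | 26-29% | 98-100% |
| 0.57 / 0 | 23 | 96-100% | 60-74% | about 100% |
| 0.57 / 0 | 46 | 98-100% | 98-100% | about 100% |

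Exchangeable correlation cancels in a site-minus-rest contrast, which favours the contrast. With neighbour correlation 0.5 (0.2 SD, N=23, uncorrected labels) the comparison is 20% against 48%.

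**Step 4: what each partial repair achieves when nothing is local**
- Continuous statistic but still a label shuffle, neighbour correlation 0.2-0.6: rejects 12-32%.
- Count kept but shuffle restricted to tested nodes, neighbour correlation 0.4, diffuse 0.3 SD, uncorrected labels: rejects 10-20%.
- Participant-level contrast with a one-sample test: 4.7-5.6%, including neighbour correlation 0.5. A separate run over more settings gave 3.5-7%.

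Only the participant-level test stays close to 5%, because each participant's contrast already carries the dependence between nodes.

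**The case against.** A reader might infer that the count test loses most of its power and would usually miss a truly local effect. The documents do not support that, for three reasons.

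- The low power figures in Step 3 belong to a shuffle over tested nodes, not to the written one. Under the written whole-brain shuffle with uncorrected labels and 0.2 SD at the site, power is 38-48% at N=23 and 62-81% at N=46. With FDR labels it remains weak (1-10%). The higher figures come from a null that also rejects when nothing is local, so they are no defence of the test, but they rule out calling it simply underpowered.
- The loss depends on node effect, node count, correlation and threshold, and the plan gives none of these for this step. At 0.57 SD confined to the site and N=46 there is no loss. In several settings the contrast shows no clear gain over the written test.
- The gate is deliberate. If no node shows an effect, there is nothing to localise, and part of the apparent failure to reject is that sequence working as intended.

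It can also be said that this is a conditional, secondary analysis that does not bear on WAB-AQ. All of this stands. It limits the power claim and the priority of the change. It does not answer the mismatch between tested nodes and shuffled nodes, which follows from the wording of section 8.4.3 whatever the effect size.

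**Conclusion.** The point holds with two parts of different weight.

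1. **Too liberal as written.** The direction follows from the text: labels come from the language network and are shuffled over the brain. The size is conditional. At a diffuse 0.3 SD, the false declaration rate is about 57-91% (uncorrected) or 21-72% (FDR), against 5%, assuming 40 language nodes, 10 at the site, in a 200-node brain. A positive result would not establish locality.
2. **Thresholding can cost power.** Against a shuffle over tested nodes, the loss runs from none (0.57 SD at the site only, N=46) to nearly all (0.2 SD with FDR labels: 0.1-6% against 48-98%). The documents do not show where in that range this trial falls.

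The change is worth making before the imaging data are analysed. The consequence is confined to the mechanistic claim about locality and the phenotype comparison built on it. The primary endpoint and its analysis are untouched.

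**What to change.** In section 8.4.3, replace the count and the label shuffle with a participant-level contrast:

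- For each participant, take the real-minus-sham hub-score change, averaged over the anterior perisylvian nodes, minus the same average over the remaining language-network nodes.
- Test that the mean contrast exceeds zero at one-sided 5%, with a period-adjusted one-sample test or a participant-level sign-flip permutation.
- Report the same contrast within each variant group for the phenotype question.
- Name in advance the atlas, the language-network nodes, the nodes that make up the site, and the threshold for the descriptive map.
- Keep the map of significant nodes as description only.

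**Cost.** New wording and a simpler calculation. No new scans are needed: Figure 1 and section 3.1.4 already schedule MRI in both periods, and section 6.4.6 makes Visit 18, the 12-week MRI, part of the crossover baseline.

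**Downsides.** Only participants scanned in both periods contribute. A regional mean dilutes an effect confined to one or two site nodes, which the descriptive map would still show. The power gain is small or absent when neighbouring nodes are correlated or effects are large. In those cases the reason for the change is control of the 5% level.
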